Participants will have the option to receive secure and encrypted text messages sent via Twilio, a third party, MGB-approved web service that integrates with REDCap to send reminders, survey invitations, and collect home practice participation over SMS text messaging. If participants prefer, study staff can send “unencrypted” texts that are not secure and could result in the unauthorized use or disclosure of their information or email reminders sent directly through REDCap. If participants want to receive communication by unencrypted texts despite these risks, they will be informed that MGB Healthcare will not be held responsible for any data breaches. These texts will not contain any protected health information. Text message and data rates may apply based on participants’ cell phone service plan. Participants have the right to refuse these texting reminders. This decision will not impact their ability to participate in the study. Participants can opt out of these text messages at any time.

Outcome Measures

Primary Outcome Measures

1. Feasibility of Recruitment

We will examine feasibility of recruitment through tracking of the number who respond through flyer (QR Code), email, website or direct clinical contact.

[Time Frame: Baseline]

2. Feasibility of Assessments

We will calculate the proportion of caregivers completing the study questionnaires.

[Time Frame: Baseline, Post-intervention]

3. Feasibility of Quantitative Measures

We will assess the proportion of quantitative measures missing within the questionnaires.

[Time Frame: Baseline, Post-intervention]

Other Pre-specified Outcome Measures

4. Symptoms of Depression

We will use the Center for Epidemiological Studies-Depression Scale (CES-D). This is a 20-item scale widely used with ADRD caregivers.

[Time Frame: Baseline, Post-intervention]

5. Mindfulness

We will use the Five Facets Mindfulness Questionnaire FFMQ (15 items) to assess caregivers' mindfulness based on 5 subscales (observing, describing, awareness, non-judging, non-reactivity).

[Time Frame: Baseline, Post-intervention]

6. Perceived Stress

We will use the PSS-10 (10 items) to assess perceived stress.

[Time Frame: Baseline, Post-intervention]

7. Symptoms of Anxiety

We will use State Trait Anxiety Inventory (STAI) state subscales (20 items) to assess anxiety symptoms in response to stressful situations. STA has been successfully used with ADRD caregivers.

[Time Frame: Baseline, Post-intervention]

8. Self-Compassion

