20. Perceptions of Email and Text Reminders

We will assess caregivers' perception of emails and text messages reminders by asking, "Do you think that the amount of emails/texts you received was: too little, just enough, too much?"

[Time Frame: Post-intervention]

21. Credibility and Expectancy

We will use the Credibility and Expectancy Questionnaire (CEQ), (6 items) to assess caregivers' perceptions that the treatment will work after participating in the intervention.

[Time Frame: Pre-intervention]

The self-report measures and assessment domains align with the purpose of the study and with recommendations for feasibility trials. Feasibility of recruitment and retention will be assessed using proportions (see Table 1). Satisfaction and credibility will be assessed with proportions of scores over the midpoint of the Client Satisfaction and Credibility and Expectancy questionnaires.

4. Subject Selection

Study Population Characteristics

Conditions or Focus of Study

- Informal caregivers of people with ADRD who endorse caregiver stress and challenges managing patient behaviors

Eligibility Criteria

Caregivers will be 18 years or older, fluent in English, who meet the criteria for an informal caregiver (e.g., family or friend of a care recipient who provides unpaid care) and lives with and cares for an individual with ADRD. The informal caregivers must have lived with the patient for more than 6 months and must currently provide more than 4 hours of supervision or direct assistance to the care recipient per day (average). Caregivers will need to endorse stress (PSS-4 \geq 6) and self-report that they had managed 1 or more behavioral symptoms in the past month. Exclusion criteria include planned change in psychotropic treatment for the duration of the study, use of mindfulness apps or any meditation (more than 60 min/week in past 6 months), major illness known to drastically worsen or require surgery for the duration of the study, active treatment for cancer, involvement in another clinical trial for caregivers, a score \geq 4 on the PMSQ and no stated concerns or distress related to care recipient's disruptive behaviors.

Inclusion Criteria

- 18 years or older
- English fluency and literacy
- Meeting criteria for being a caregiver (e.g., family or friend of a care recipient who provides unpaid care)
- Must live with and care for an individual with ADRD.
- Must have been in a caregiver role for more than 6 months

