It is unlikely that participants will incur any risk of physical harm because of study participation. Participants may find some questionnaire items to be emotionally upsetting or may experience psychological discomfort while discussing their experiences during intervention sessions. The study MPI [name] is a licensed psychologist and the study MPI [name] is a geriatrician. Both have expertise with ADRD caregivers and will triage and refer individual participants to an appropriate level of clinical care, as needed.

Communication-related risks: Text messages by mobile/cellphones are a common form of communication. The SOCIAL research study involves sending participants text messages using the Twilio app. Participants do not have to agree with receiving text messages in order to participate. These text messages will include information about session reminders, reminders to complete homework logs, and activity prompts to complete before upcoming sessions. We will send these messages daily during the 6-week group intervention. Texting over mobile/cell phones carries security risks because text messages between mobile/cellphones are not encrypted. This means that information you send or receive by text

message could be intercepted or viewed by someone other than staff involved with this research study, or by your mobile/cellphone provider or carrier.

Meditation-related risks. Meditation may cause study participants to feel emotions more intensely on a temporary basis (during practice) as the practice of meditation teaches participants to become more mindful of their thoughts, feelings, and emotions. Participants will learn through the instruction materials that this increase is temporary and is associated with an actual decrease in symptoms over time, due to habituation. If subjects report ongoing emotional dysregulation, the MPI, [name] will triage and refer individual participants to an appropriate level of clinical care, as needed.

8. Benefits

Potential Benefits of the Proposed Research to Human Subjects and Others

Participants may benefit from the numerous evidence-based advantages associated with engaging in meditation, self-compassion and training in managing challenging care recipient behaviors. Caregivers may experience reduced caregiving stress, emotional distress, and improved well-being. Caregivers may be able to better regulate their emotions, have fewer ruminating thoughts, and provide higher quality care to their loved ones.

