We will also explore pre-post changes in our intervention targets (mindfulness, self-compassion, caregiver self-efficacy and social support) and outcomes (stress, depression, anxiety, and well-being) using t-tests and explore correlations between change scores and outcomes. We will revise our procedure, conceptual model and measures based on quantitative and qualitative data as needed. Consistent with recent recommendations we will report whether the MCID for each quantitative measure is included within the 95% confidence interval for all quantitative analyses as a go/no go benchmark rather than statistical significance.

10. Monitoring and Quality Assurance

Data Safety and Monitoring Plan

Participant Confidentiality. All study materials will identify participants only by study ID, visit number, and visit date. The study research assistant will be trained in procedures to protect study participant confidentiality. Recordings of each session will be immediately de-identified (e.g., only ID, visit number and date) and stored on a password protected computer; the recording will be subsequently and immediately deleted from the recording device.

Group sessions will also be audio-recorded and transcribed. The names of the people who volunteer for this study will not be discussed outside of this project. Identities will be kept confidential. When the audio recordings are being transcribed, participants' names will be replaced with a code. Only trained members of the research team will have access to and know which code belongs to whom. These codes will be stored within the Mass General Brigham firewall, which is secure, and password protected.

Data Validity and Security. The research team will develop standard operating procedures for data collection, data management, and quality control. The project manager, under the supervision of the MPIs will oversee all procedures related to secure data collection and management. Data activities will be conducted using Research Electronic Data Capture (REDCap), a software and workflow tool for research data collection and management, with assistance from Partners HealthCare Research Computing, Enterprise Research Infrastructure & Services (ERIS) group. REDCap provides secure web-based applications with an intuitive user interface data and real time validation rules.

11. Privacy and Confidentiality

- Study procedures will be conducted in a private setting

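### Distress from meditation is a risk the protocol names, but the only detection it describes is caregiver report, and no outcome counts harm or individual worsening

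*Combined protocol and SAP*

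**What the plan says.** - **The risk (section 7, Meditation-related risks).** The protocol foresees that emotions may be felt more strongly for a time during practice. It adds: "Participants will learn through the instruction materials that this increase is temporary and is associated with an actual decrease in symptoms over time". The response that follows begins "If subjects report ongoing emotional dysregulation", in which case an investigator arranges triage.
- **The general route (section 7, opening paragraph).** For upsetting questionnaire items or discomfort in sessions, the two lead investigators "will triage and refer individual participants to an appropriate level of clinical care, as needed". How they would learn of the need, and whether cases are recorded or counted, is not described.
- **Outcomes (section 3, Outcome Measures).** There are 21 items, 3 primary and 18 other pre-specified. None is labelled harm, safety, adverse events or tolerability. CES-D, STAI state, PSS-10, the WHO well-being index and the NPI caregiver distress scale are collected at baseline and post-intervention. A two-item rating of perceived change in stress is collected post-intervention.
- **Monitoring (section 10).** The text headed "Data Safety and Monitoring Plan" deals with confidentiality, data validity and data security. It does not define, collect or review adverse events.
- **Analysis (section 9).** Stress, depression, anxiety and well-being are examined by t-tests on pre-post change. Correlations of change scores are also explored. The go/no-go benchmark is whether the MCID lies in the 95% confidence interval.
- **Exit interview (section 6).** It is individual, lasts 30 minutes and takes place after week 6. The listed topics do not name distress or adverse effects.

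**The concern.** The protocol identifies a specific psychological risk in people enrolled because they are already stressed, yet it describes no scheduled question about that risk. Detection depends on a caregiver deciding that the distress is ongoing and then saying so. The same paragraph says the materials will present the intensified emotion as passing and as linked to fewer symptoms later. The text does not say where temporary ends and ongoing begins.

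Two things are at stake. First, the pilot is meant to refine the intervention and settle it before a pilot RCT. If few or no caregivers volunteer distress, the team cannot tell a true low rate from a rate nobody asked about. Second, the data that could reveal deterioration are summarised as averages, so some caregivers could worsen without this appearing in any planned result.

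**Working it through.** The plan gives no event rate, power or derived sample size, so there is no figure to reproduce. Twenty is a cap, not a calculated number. Event rates, capture shares and effect sizes below are assumptions for scale.

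**1. Count of outcomes.** Items 1 to 21 were checked. Designated for harm: 0. Pre-post scales on which distress or well-being could worsen: 5 (CES-D, STAI, PSS-10, WHO well-being, NPI distress). Section 9 names stress, depression, anxiety and well-being for the t-tests; it sets no individual-worsening rule for any scale.

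**2. Effect of relying on volunteered reports.** Let p be the true proportion affected, s the share of affected caregivers whose distress is recorded, and n = 20. The chance of recording at least one case is 1 − (1 − ps)^20.

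| True rate p | s = 100% | s = 50% | s = 25% |
|---|---|---|---|
| 5% | 64.2% | 39.7% | 22.2% |
| 10% | 87.8% | 64.2% | 39.7% |
| 20% | 98.8% | 87.8% | 64.2% |

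For example, with p = 10% and s = 50%: 1 − 0.95^20 = 0.642.

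**3. What zero reports would exclude.** With full capture, the one-sided upper 95% limit is 1 − 0.05^(1/n), and the upper end of the two-sided exact interval is 1 − 0.025^(1/n).

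| n | One-sided | Two-sided |
|---|---|---|
| 20 | 13.9% | 16.8% |
| 16 | 17.1% | 20.6% |
| 10 | 25.9% | 30.8% |

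With partial capture the data bound only ps, so the limit on p is the full-capture limit divided by s. At n = 20 the one-sided limit becomes 0.139/0.50 = 27.8% for s = 50%, and 0.139/0.25 = 55.6% for s = 25%. For s at or below 0.139 it reaches 100%. Under the plan s is unknown, so no limit can be claimed.

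**4. What a mean can hide.** Suppose 3 of 20 worsen by 1 SD and 17 improve by 0.5 SD. The mean improvement is (17 × 0.5 − 3 × 1)/20 = (8.5 − 3)/20 = 0.275 SD. With 2 worsening it is (9 − 2)/20 = 0.35 SD, and with 4 it is (8 − 4)/20 = 0.20 SD. In each case the planned summary shows benefit while 10% to 20% have deteriorated.

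**5. Timing.** The scales are taken only before and after the six weeks. No score is linked to the triage route in section 7. A caregiver who leaves because of distress may give no post-intervention score or exit interview, and section 9 does not say how such cases are reported.

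**The case against.** The strongest reply is that the study is not blind to harm, and several stronger readings that a reader might infer do go too far.

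- *No outcome can record harm.* The documents do not support this. Five pre-post scales can worsen, and caregivers also rate perceived change. The gap is that none is designated for harm and no individual-worsening count is planned.
- *Caregiver report is the only route to triage.* This is too broad. The opening paragraph of section 7 has a second, as-needed route that does not hinge on the word ongoing, and a trained clinical social worker leads each live session. The narrower statement stands: for meditation-related distress, self-report is the only detection described.
- *Nobody asks about distress.* This cannot be established. The items of the home-practice log and the interview guide are not reproduced, and distress could arise under barriers to skill practice.
- *The materials discourage reporting.* This is inference. Telling caregivers that the effect is temporary might equally help them recognise that lasting distress is unusual.
- *The pilot fails to show tolerability.* Tolerability is not a stated aim. Hypothesis 1 names feasibility, acceptability, credibility and fidelity, and no passage says SOCIAL will proceed because no problems were reported.

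It is also fair that 20 caregivers without a control arm can bound a rate only loosely, and that worsening cannot be attributed to SOCIAL. What remains is that the plan describes no solicited count, no individual-level summary and no harm element in the go/no-go benchmark.

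**Conclusion.** The point holds as a gap in data capture and reporting. For a risk the protocol itself names, the described detection is passive, no listed outcome is designated for harm, and the scales that could reveal deterioration are summarised only as group change. Followed as written, silence about distress is uninformative when SOCIAL is finalised, and a mean gain of 0.275 SD is compatible with 3 of 20 caregivers worsening by 1 SD.

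The size depends on assumed rates and capture shares, since the documents give none. With full capture, 0 of 20 would bound the rate at 13.9% one-sided; without systematic asking no bound applies. The change is worth making but does not put the pilot's feasibility aims in doubt.

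The opening part of the document and Table 1, cited after the outcome list, are not in the text reviewed. The conclusion assumes that neither contains a harms outcome, and that the log and interview guide have no distress item.

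**What to change.** 1. **Solicited item.** Add one yes/no question to the existing weekly home-practice log, asking about distress that the caregiver attributes to practice or a session. List as an outcome the number of caregivers with at least one yes and the number triaged or referred, each with an exact 95% interval and the number who returned logs as denominator.
2. **Individual worsening.** Report the number and proportion whose CES-D, STAI or PSS-10 worsened from baseline, with exact 95% intervals, and beside them the number lacking a post-intervention score. Since measurement error alone will move some scores in the wrong direction, show both any worsening and worsening by at least the MCID that section 9 already intends to use (the documents give no MCID values). Describe these counts as uncontrolled.
3. **Reconcile section 7.** The investigators should reconcile the message that intensified emotion is temporary with the reporting route in the same paragraph. The wording, and the clinical handling of a yes, are theirs to decide.

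The cost is one extra item a week, an added outcome line, two tabulations of data already collected, some follow-up contacts and possibly a less favourable figure to report. No change in sample size is needed.

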Addressing stress, emotional functioning, and well-being in caregivers of persons with ADRD is a public health concern. Addressing caregivers’ stress is important not only for decreasing own risk for chronic health problems, morbidity, and mortality, but also because it affects the quality of care they provide and thus their loved one’s emotional and health outcomes.^{5,6} As such, there is a need for feasible, acceptable, effective, and scalable stress management programs to prevent the deleterious effect of stress on both caregivers’ and their loved one’s overall health. Studies show that on average, 42- 55% of ADRD caregivers are actively looking for non-pharmacological interventions to decrease caregiver stress.⁸

Available programs do not meet the psychological and practical needs of stressed caregivers of persons with ADRD; we need better solutions. First, while helpful, most support groups do not systematically teach behavioral management skills which caregivers report needing in order to manage challenging patient behaviors.⁹ Second, behavioral management skills interventions exist, but do not teach: 1) emotional regulation skills which are necessary in order to foster caregiver ability to access and use these skills to manage patient behaviors, and/or 2) self-compassion and compassion skills which are necessary to bypass guilt and loneliness and navigate behavioral symptoms which are common caregiver challenges. Third, mindfulness and self-compassion interventions are effective solutions for managing stress, and distress across multiple populations, but engagement and efficacy among diverse ADRD caregivers are limited.¹⁰⁻¹⁵

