Building on the limitations of prior research, we proposed to develop the **Supporting Our Caregivers In ADRD Learning (SOCIAL)** to help caregivers of persons with ADRD manage the stress associated with the general caregiver experience including stress stemming from managing challenging patient behaviors. In AIM 1 of the SOCIAL study (Protocol#: 2022P002037) we obtained feedback on the program's proposed content and format from caregivers of individuals living with ADRD. What we learned from those responses was used to inform this open pilot (aim 2) of the study which aims to teach: (1) mindfulness skills; (2) compassion and self-compassion skills; and (3) behavioral management skills. The SOCIAL open-pilot also provides psychoeducation and group-based training and skill practice to facilitate skill uptake and integration within the caregiver experience and tasks.

2. Specific Aims and Objectives

We will conduct a live video open pilot of the SOCIAL intervention with exit interviews (N=up to 2 groups, up to 20 caregivers). We will use this information to revise SOCIAL and our conceptual model, as needed to maximize feasibility and target engagement. Hyp. 1: SOCIAL will show evidence of feasibility, acceptability, credibility, and fidelity. Hyp. 2. SOCIAL will show evidence of improvement in intervention targets and outcomes and these improvements will be correlated.

3. General Description of Study Design

We will conduct an open pilot of our active intervention, SOCIAL, delivered via live video (Zoom) to ADRD caregivers who meet eligibility criteria. We will recruit and enroll up to 20 stressed informal caregivers of ADRD individuals who also report challenges managing patient behaviors. Participants will be adults (18 years or older) who care for an individual with ADRD and who endorse caregiver stress on the Perceived Stress Scale-4 (score of 6 or higher) and have managed 1 or more behavioral symptoms in the past month. We will recruit caregivers from an array of sources, including, but not limited to, local caregiver support programs, dementia research centers, and community partners. All recruitment efforts will be captured in a secure database and will allow us to solidify our recruitment plan for the subsequent pilot clinical trial.

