The Self-Compassion Scale-Short Form (SCS-SF), (12 items)assesses self-kindness.

[Time Frame: Baseline, Post-intervention]

9. Compassion

The Compassion Scale (CS) (16 items) assesses common humanity, kindness toward others and ability to understand the suffering or challenges of others.

[Time Frame: Baseline, Post-intervention]

10. Caregiver self-efficacy

The Revised Caregiver self-efficacy instrument (10 Items) assesses domains of self-efficacy including obtaining respite, responding to disruptive patient behaviors, and controlling upsetting thoughts.

[Time Frame: Baseline, Post-intervention]

11. Loneliness

The UCLA Loneliness scale (3-item) assesses relational connectedness, social connectedness, and self-perceived isolation.

[Time Frame: Baseline, Post-intervention]

12. Social Support

Interpersonal Support Evaluation List short form, ISEL(12 items) assesses appraisal, belonging and tangible social support.

[Time Frame: Baseline, Post-intervention]

13. Well-being

The World Health Organization-Five Well-Being Index (WHO-D) (5 items) assesses emotional well-being.

[Time Frame: Baseline, Post-intervention]

14. Distress Due to Patient Challenges Behaviors

The Neuropsychiatric Inventory Caregiver Distress Scale (12 items) assesses distress associated with dementia patient's behaviors such as apathy, elation, disinhibition.

[Time Frame: Baseline, Post-intervention]

15. Satisfaction with the Intervention

We will use the Client Satisfaction Questionnaire (CSQ-3) to assess caregivers' satisfaction with the intervention.

[Time Frame: Post-intervention]

16. Perceptions of improvement

We will use the Modified Perception of Global Improvement (MPGI), (2 items) to measure a participant's interpretation of changes in perceptions of stress following intervention.

[Time Frame: Post-intervention]

17. Therapist Fidelity

We will assess both therapists' ability to deliver the content of each session (through therapist completed adherence checklists) and therapist fidelity (through independent review of recorded sessions by Co-I's)

[Time Frame: Baseline through Post-intervention]

18. Perceptions of Questionnaire Battery

We will assess how appropriately the caregivers fill the questionnaires through documenting completion rates of all questionnaires.

[Time Frame: Post-intervention]

19. Adherence to Home practice

We will report the proportion of caregivers who complete weekly home practice.

[Time Frame: Weekly]

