Importance of the Knowledge to be Gained

The larger goal of this research is to provide ADRD caregivers with feasible and scalable resources they need to navigate the stress and challenges managing patient behaviors. The current R01 pilot feasibility RCT represents the first step toward this larger goal, by allowing us to ascertain feasibility, mechanism and proof of concept necessary in order to conduct a scientifically rigorous stage II efficacy trial.

Remuneration

Participants will be remunerated \$20 at base line for enrollment data collection and \$40 at completion of intervention at their Exit Interview. Participants can receive up to \$60 by check. If participants do not want to provide their Social Security Number, they will be provided the option to receive \$50 in gift cards, distributed as a \$20 baseline and then \$30 gift card upon study completion in compliance of the MGH policy, "Payment to Human Subjects for Participation in Research."

9. Statistical Analysis

Sample Size and power analyses

Traditional power analyses are also not appropriate for activities within NIH stage 1A, where the goal is to "explore" feasibility and mechanistic target engagement for the sole purpose of refining the intervention and protocol. Although these studies are inherently underpowered for detecting statistical significance, they provide essential information on feasibility, signal of improvement in targets and outcomes, and signal of association between change in targets and outcomes.¹⁸

Optimize SOCIAL

Qualitative exit interview data will be analyzed using Nvivo12, which assessed reliability (kappa) of coding for themes and patterns of responses. A postdoctoral fellow and/or the RAs, under the supervision of the MPIs, will code qualitative data into superordinate themes and subthemes. The research assistant will complete reliability coding. Discrepancies will be resolved through discussions until reliability is obtained

($\kappa > .80$). We will use qualitative thematic analyses with a hybrid deductive-inductive analyses plan. Inductive analyses will be guided by the Framework method.

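### Do the three baseline/post scales left out of the target and outcome lists (compassion, loneliness, behaviour-related distress) leave a gap in the Hypothesis 2 analysis?

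*Combined protocol and SAP*

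**What the plan says.** Hypothesis 2 in Section 2 reads: "SOCIAL will show evidence of improvement in intervention targets and outcomes and these improvements will be correlated". Section 9, under Optimize SOCIAL, puts this into practice with t-tests and exploratory correlations, and sets out in parentheses which constructs count as "intervention targets (mindfulness, self-compassion, caregiver self-efficacy and social support) and outcomes (stress, depression, anxiety, and well-being) using t-tests". The same paragraph adds that, for each quantitative measure, the report will say whether the minimal clinically important difference (MCID) lies inside the 95% confidence interval. It then states the use of the results: "We will revise our procedure, conceptual model and measures based on quantitative and qualitative data as needed".

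Section 3 lists eleven scales with both baseline and post-intervention time frames (items 4 to 14), under a heading that makes them other pre-specified outcome measures. Compassion is item 9, loneliness item 11, and distress from patient behaviours item 14: "The Neuropsychiatric Inventory Caregiver Distress Scale (12 items) assesses distress associated with dementia".

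On purpose, the Current study section says that SOCIAL is to help caregivers "manage the stress associated with the general caregiver experience including stress stemming from managing challenging patient behaviors" and that the pilot "aims to teach: (1) mindfulness skills; (2) compassion and self-compassion skills; and (3) behavioral management skills". Section 8 returns to the need to "navigate the stress and challenges managing patient behaviors".

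**The concern.** Eligibility depends on having managed behavioural symptoms and on having some concern or distress about them, and Week 4 of the programme teaches behaviour management. Yet the only scale devoted to distress from those behaviours is not a named Hypothesis 2 outcome; all four named outcomes are general. Caregiver self-efficacy has a domain on disruptive behaviours, but it is a target, so no behaviour-specific outcome stands opposite it.

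The Significance section also argues for "self-compassion and compassion skills which are necessary to bypass guilt and loneliness and navigate behavioral symptoms which are common caregiver challenges". Compassion is taught and measured, and loneliness is measured, but neither enters the listed target-outcome comparisons.

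The correlations feed the revision of the conceptual model. If they speak only to general stress, depression, anxiety and well-being, they cannot show whether gains in skills go with less behaviour-related distress or loneliness. A later choice of which extra pairs to report could then be guided by the data.

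**Working it through.** The documents give no power, alpha or sample size calculation to reproduce, so the check is a count, a comparison of passages and a precision calculation.

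**Count of scales**
- Section 3, items 4 to 14: depression, mindfulness, stress, anxiety, self-compassion, compassion, self-efficacy, loneliness, social support, well-being, NPI distress = 11.
- Named in Section 9: 4 targets + 4 outcomes = 8.
- Not named: 11 - 8 = 3 (compassion, loneliness, NPI distress).
- Target-outcome pairs, if every listed target is crossed with every listed outcome: 4 x 4 = 16, none with a behaviour-specific outcome. The plan does not state the figure 16; it is inferred from the two lists.

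**Are the three scales without a role?** No. Section 3 pre-specifies them as outcome measures. The MCID sentence refers to each quantitative measure, which most naturally takes in all eleven, though its closing reference to all quantitative analyses leaves a little doubt. What they lack is only a label as target or outcome for Hypothesis 2.

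**Are the four named outcomes a poor match to the aim?** Set side by side:
- Significance names the problem as stress, emotional distress (depressive and anxiety symptoms) and reduced well-being, made worse by behavioural symptoms.
- Section 8 expects benefit in stress, emotional distress and well-being.
- Section 9 analyses stress, depression, anxiety and well-being.

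These agree. The Current study section places behaviour-related stress within the general caregiving experience, so a general stress scale is a defensible outcome.

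**Does the rationale require particular extra pairs?** Two skills (self-compassion, compassion) crossed with two end points (loneliness, NPI distress) would give 2 x 2 = 4 pairs, none among the 16. That count depends on the reading. The opening background ties only self-compassion to guilt and loneliness; on that version one pair has scales. Guilt has no dedicated scale in the battery. Navigating behavioural symptoms is a capability, and the self-efficacy scale is arguably as close to it as NPI distress. The documents do not fix a set of required pairs.

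**What would extra correlations tell us?** The Fisher interval is tanh(atanh(r) ± 1.96/√(n - 3)).
- n = 20 (the planned maximum), r = 0.50: tanh(0.549 ± 0.475) = 0.07 to 0.77.
- n = 20, r = 0.30: tanh(0.310 ± 0.475) = -0.16 to 0.66.
- n = 16 (assuming 20% loss; the plan gives no rate), r = 0.50: tanh(0.549 ± 0.544) = 0.01 to 0.80.

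Adding compassion as a target, and loneliness and NPI distress as outcomes, would enlarge the grid to 5 x 6 = 30 pairs, each about this imprecise.

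**The case for a change.** The best case for a change is that it costs a sentence or two and needs no new data, and that labelling the scales beforehand prevents selective reporting. An MCID reading of a change score is not a correlation, so the association half of Hypothesis 2 omits the three scales however that sentence is read. The heading in Section 3 does not settle the matter either, because it also covers the four constructs that Section 9 calls targets. And imprecision at this sample size weakens the listed correlations just as much as any added ones.

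Most of this stands as description: the three scales are outside the listed correlations, and a sentence saying how they are used would be tidy. It does not show that the plan as written goes wrong. Labelling the scales descriptive only would fully answer the point while altering no result, which marks it as a matter of documentation. The risk of selective reporting is small where the analysis is openly exploratory and no decision depends on these correlations; any further pair can be reported as one that Section 9 did not list. Model revision also draws on the exit interviews in Section 6, which cover the intervention components, the applicability of the measures and skill practice.

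**Conclusion.** No change is needed. Three of eleven baseline/post scales are not assigned as target or outcome for Hypothesis 2, and no listed target-outcome correlation has a behaviour-specific outcome. This is a gap that analysts can fill sensibly: report paired change with a 95% interval for all eleven scales, as the MCID sentence already suggests, and treat any correlation involving the three as supplementary. The eight named scales, the feasibility primary outcomes and every stated figure are unaffected, and no rule combines the measures into one decision.

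The conclusion assumes that the MCID sentence covers every scale, that the correlations remain exploratory signals in a pilot of at most 20, and that no go/no-go decision comes to rest on them. Which outcomes belong in the model would deserve a fresh look for the later randomised pilot, where a mechanism claim would carry more weight.
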